## 2 STUDY OBJECTIVE

The purpose of this study is to evaluate the long-term safety and effectiveness of the OMNI® Surgical System in subjects who were treated with the OMNI Surgical System in combination with Cataract Extraction, at least 700 days prior to enrollment.

## 3 BACKGROUND AND JUSTIFICATION FOR THE STUDY

Glaucoma is a progressive disease leading to irreversible damage to retinal ganglion cells with the global burden expected to rise to 111.8 million people by the year 2040. Primary open angle glaucoma (POAG) is the most prevalent form of glaucoma and elevated IOP is the only treatable risk factor. Hypotensive eye drops are commonly used as the first line clinical management for POAG. Ocular side effects, such as allergies, ocular surface disorders, blepharitis, pemphigoid, and abnormal pigmentation, and systemic side effects, such as bradycardia, headaches, depression, anxiety, confusion, dysarthria, hallucinations, lethargy, polyuria, weight loss, and metabolic acidosis, can occur during long term use of topical medications. There is also a documented low rate of compliance with eye drops that increases the risk of disease progression and loss of vision.

The Ocular Hypertension Treatment Study showed that reduction of IOP by an average of 22.5% through medical intervention decreased conversion from ocular hypertension to glaucoma over a 5-year period to approximately half that of untreated controls (4.4 vs. 9.5%). Similarly, the Early Manifest Glaucoma Trial (EMGT) showed that treatment of newly diagnosed POAG with argon laser trabeculoplasty plus betaxolol reduced the risk of disease progression at 6 years to half of that for untreated controls (hazard ratio, 0.50; 95% confidence interval, 0.35–0.71). Each mmHg of IOP reduction decreased the risk of progression by approximately 10%.

 [REDACTED]

 [REDACTED]

 [REDACTED]

 [REDACTED]

 [REDACTED]

 [REDACTED]

 [REDACTED]

The Advanced Glaucoma Intervention Study (AGIS) showed that eyes with 100% of visits with IOP less than 18 mmHg over 6 years had mean changes from baseline in visual field defect score close to zero during follow-up.

*Note: A summary of known and potential risks to humans, as identified in the literature or through preclinical testing and/or prior clinical evaluations for the study devices can be found in the Instructions for Use for the OMNI Surgical System.*

This is a multicenter, observational clinical study with no planned surgical intervention. Both prospective and retrospective data on participating subjects will be collected in the study.

## 4 STUDY DEVICE

## 4.1 DEVICE DESCRIPTION

The OMNI® Surgical System (“OMNI”) is indicated for canaloplasty (microcatheterization and transluminal viscodilation of Schlemm's canal) followed by trabeculotomy (cutting of trabecular meshwork) to reduce IOP in adult patients with POAG.

17

## 4.2 TRAINING

All surgeons would have received training in accordance with Sight Sciences, Inc.'s requirement for using the OMNI Surgical System. OMNI surgery will not be conducted in this trial therefore study specific training on the device will not be required.

## 5 STUDY DESIGN

This is a multicenter, observational research study with no planned surgical interventions. Both prospective and retrospective data on participating subjects will be collected in the study. Up to 130 subjects will be enrolled. Subjects will be followed from 24-months (700 – 1040 days) through 36-months (1,050 – 1,110 days) post-surgery. Pre-operative and surgery data will be collected retrospectively.

Prospective data will be collected for all study specific post-operative visits following enrollment into the study.

The study will employ a medication washout at the 24-, and 36-month endpoints for the subjects who received medication washout prior to the OMNI procedure and are using hypotensive medications at those visits.

## 5.1 STUDY SITES

This clinical study will be conducted at up to 15 sites in the United States.

## 6 STUDY ENDPOINTS

### 6.1 PRIMARY SAFETY ENDPOINT

Rate of occurrence of sight-threatening adverse events (AEs)

#### 6.1.1 SECONDARY SAFETY ENDPOINTS

- Rate of ocular AEs
- Reduction in best corrected distance visual acuity (BCVA) from baseline
- Secondary Ocular Surgical Interventions, including laser, for IOP control

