## 7.2 EXCLUSION CRITERIA

## 8 STUDY PROCEDURES

### 8.1 STUDY SCHEDULE – PRE-OPERATIVE WASHOUT (SUBJECTS THAT UNDERWENT MEDICATION WASHOUT PRIOR TO OMNI)

Table 1: Study Visit Schedule

*Note: The fellow eye should be followed per the PI's usual practice based on the ocular health of the fellow eye.*

PROCEDURE	RETROSPECTIVE DATA			OBSERVATIONAL PROSPECTIVE DATA			
	PRE-WASHOUT (DAY -45 TO -6)	POST-WASHOUT (DAY -6 TO 0)	OMNI SURGERY (DAY 0)	24 M  (DAY 700-1,040)	24 M WASHOUT  (DAY 700-1,040)	36 M (DAY 1,050-1,110)	36 M WASHOUT  (DAY 1,050-1,110)
Informed Consent and demographics 				X		X	
Medical & Ocular History	X	X		X	X	X	X
Medication Log 	X	X		X	X	X	X
Monocular BCVA 	X	X		X	X	X	X
Visual Field (Humphrey 24-2 SITA)	X			X		X	
IOP (Goldmann) 	X	X		X	X	X	X
Slit Lamp Exam	X	X		X		X	
Gonioscopy	X			X		X	
Dilated Fundus Exam/C:D Ratio	X			X		X	
Surgery			X				
Adverse Events	X	X	X	X	X	X	X

1.   

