## 8.2 STUDY SCHEDULE – No PRE-OPERATIVE WASHOUT

**Table 2: Study Visit Schedule**

*Note: The fellow eye should be followed per the PI's usual practice based on the ocular health of the fellow eye.*

PROCEDURE	RETROSPECTIVE DATA		OBSERVATIONAL PROSPECTIVE DATA	
	PRE-SURGERY BASELINE (DAY -45 TO -6)	OMNI SURGERY (DAY 0)	24 M  (DAY 700-1040)	36 M (DAY 1,050-1,110)
Informed Consent and demographics 			X	
Medical & Ocular History	X		X	X
Medication Log 	X		X	X
Monocular BCVA 	X		X	X
Visual Field 	X		X	X
IOP (Goldmann) 	X		X	X
Slit Lamp Exam	X		X	X
Gonioscopy	X		X	X
Dilated Fundus Exam/C:D Ratio	X		X	X
Surgery		X		
Adverse Events	X	X	X	X

1. 

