### 10.5.2 BEST CORRECTED VISUAL ACUITY

The number and percent of eyes reporting with BCVA of 20/20 or better, 20/25 or better, 20/32 or better, 20/40 or better, worse than 20/40 to 20/80, worse than 20/80 to 20/200, and worse than 20/200 at each visit will be summarized. The number and percent of eyes reporting BCVA of increase  $\geq$  10 letters, increase 10 letters, increase  $\geq$  5 letters to < 10 letters, within 5 letters change, decrease  $\geq$  5 letters to < 10 letters, decrease 10 letters, and decrease  $\geq$  10 letters at each postoperative visit will be calculated.

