### 17.2 BEST CORRECTED VISUAL ACUITY

Best corrected visual acuity (BCVA) will be collected using the same method that was used at the pre-surgery baseline visit. For the prospective scheduled study visits, a manifest refraction should be conducted if the initial BCVA acquired is  $\geq 2$  lines worse compared to the pre-surgery baseline. If the BCVA continues to be  $\geq 2$  lines worse compared to baseline even after manifest refraction, pinhole visual acuity should be completed.

In order to provide a standardized and well-controlled assessment of visual acuity, visual acuity assessments for all subjects should be performed under consistent conditions (e.g., the same lighting conditions, viewing distance, etc.) at each visit.

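### The BCVA reduction endpoint starts from a pre-surgery value although every eye then had its cataract removed, so it understates vision loss after surgery; no within-eye 24-to-36-month change is planned

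*Combined protocol and SAP*

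**What the plan says.** Section 6.1.1 lists "Reduction in best corrected distance visual acuity (BCVA) from baseline" among the secondary safety endpoints, and the synopsis and 10.6 repeat it. Neither 6.1.1 nor 10.5.2 says which visit is the baseline.

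Elsewhere the only baseline described is pre-surgical:

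- Table 2 (Cohort B) labels the visit "PRE-SURGERY BASELINE (DAY -45 TO -6" days.
- Table 1 (Cohort A) has BCVA at "PRE-WASHOUT (DAY -45 TO -6" days and again after washout, both before day 0.
- Appendix A, 17.2, states: "Best corrected visual acuity (BCVA) will be collected using the same method that was used at the pre-surgery baseline visit". It asks for a manifest refraction when acuity is two or more "lines worse compared to the pre-surgery baseline".

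Section 2 restricts the study to subjects "treated with the OMNI Surgical System in combination with Cataract Extraction, at least 700 days prior to enrollment". The lens is therefore removed between the baseline and every later BCVA.

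On the source of earlier data, Section 5 says: "Pre-operative and surgery data will be collected retrospectively". Section 8.6 agrees. The first post-operative BCVA in either schedule is at the 24-month visit (day 700 to 1,040), and the next is at 36 months (day 1,050 to 1,110).

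Section 10.5.2 plans two BCVA tables. One counts eyes in absolute acuity bands at each visit. The other counts eyes by letter change at each post-operative visit, with a middle category of "within 5 letters change". No change between 24 and 36 months is planned.

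**The concern.** Cataract extraction is expected to improve acuity. If the reference was taken while the cataract was still present, each eye's recorded change is the gain from cataract removal less anything lost afterwards. The two cannot be separated in this endpoint, and for any positive gain the error has one direction: loss after surgery looks smaller than it was.

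The study's purpose is long-term safety after a combined procedure. A reader of the final report would naturally take a low rate of BCVA reduction as evidence that vision was stable over the follow-up period. The endpoint as set up does not show that.

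**Working it through.** The plan states no rate, threshold or sample size for BCVA, so there is no figure of its own to reproduce. The check is on the reference point.

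**Inputs.** From the documents: the pre-surgery reference (Tables 1 and 2; 17.2), cataract extraction in every eye (Section 2), the category for a decrease of at least 10 letters (10.5.2), and the visit windows (Section 5). Assumed: the cataract gain G, because the documents give neither a baseline BCVA nor an expected gain.

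**Fixed gain.** Let L be the letters lost from the eye's post-operative level.

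- Recorded decrease from the pre-surgery value = L − G.
- It reaches 10 letters only if L − G ≥ 10, that is L ≥ 10 + G.

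| Assumed G (letters) | Post-operative loss needed (letters) |
|---|---|
| 5 | 10 + 5 = 15 |
| 10 | 10 + 10 = 20 |
| 20 | 10 + 20 = 30 |

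An eye that gains 15 letters and later loses 15 has a net change of 15 − 15 = 0. It falls in the middle category of 10.5.2.

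**Gain that varies between eyes.** Suppose G is normal with mean m and standard deviation s (both assumed). The share of eyes with true loss L that is recorded as a decrease of at least 10 letters is P(G ≤ L − 10) = Φ((L − 10 − m)/s). The ranges below are for s from 5 to 10 letters.

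| True loss L | m = 5 | m = 10 | m = 15 |
|---|---|---|---|
| 10 letters | 16–31% | 2–16% | 0.1–7% |
| 15 letters | 50% | 16–31% | 2–16% |

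For example, L = 10, m = 5, s = 5 gives Φ(−1) = 16%, and s = 10 gives Φ(−0.5) = 31%. Against a post-operative reference, and leaving measurement error aside, every one of these eyes would be counted.

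**What the other planned summaries show.**

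- *Absolute bands (10.5.2).* A cataract gain cannot hide a poor absolute acuity here. But the bands are counts per visit: an eye that falls out of a band can be replaced by one that rises into it, and no eye is followed from one visit to the next.
- *Fundus, slit lamp, gonioscopy and visual field (10.5.3).* These may show the cause of a loss. They do not measure acuity change.
- *Adverse events (Section 9).* Post-operative events up to enrollment are collected, and a condition present at enrollment counts as an event if it becomes more severe. Enrollment is at least 700 days after surgery, so worsening is judged from a state without the cataract. This depends on the investigator recognising and reporting the event; it is not a tabulated letter change.

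**Interval available for a 24-to-36-month comparison.** Shortest: 1,050 − 1,040 = 10 days. Longest: 1,110 − 700 = 410 days.

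**The case against.** The strongest reply has three parts.

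First, change from pre-operative acuity answers a legitimate question, namely whether the combined procedure left the eye worse than before. The study is descriptive by its own account (10.1), BCVA is a secondary safety endpoint, and no hypothesis hangs on it. This stands, and is why the present endpoint should be kept.

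Second, 6.1.1 and 10.5.2 do not name the reference visit. The BCVA footnotes to Tables 1 and 2 are absent from the available text, and the list of anticipated adverse events in 9.2 is blacked out. A definition, or an acuity-loss event judged from a post-operative value, may be there. This also stands. The pre-surgery reference in the letter-change table is the natural reading, not a stated one.

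Third, a reader might infer that late vision loss is cancelled out in the study as a whole. The documents do not support that. Absolute bands, ocular examinations, visual fields and adverse event reporting each give loss some route into the report. What they lack is a within-eye acuity change from a value taken after the cataract was removed.

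Two stronger remedies are also tempting. One is to measure loss from the best post-operative BCVA in the chart. Retrospective extraction covers only pre-operative and surgery data for this purpose, so that would need new extraction. Choosing the highest of several unstandardised readings would also exaggerate later loss through regression to the mean. The other is to change the refraction trigger in 17.2. At the 24-month visit the plan holds no earlier post-operative value to compare with, and the gap in the analysis can be closed without touching that procedure.

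**Conclusion.** The point holds for the BCVA reduction endpoint and, on the natural reading, for the letter-change table. Both set later acuity against a value from before cataract removal, and no within-eye comparison from a later reference is planned. For any positive gain G, a recorded decrease of 10 letters or more requires a post-operative loss of 10 + G letters: 15, 20 or 30 for assumed gains of 5, 10 or 20.

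The direction rests on one inference, that the cataract lowered BCVA before surgery. The size is unknown because G is not documented. The understatement belongs to this endpoint; it does not follow that the study as a whole cannot detect vision loss.

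**What to change.** 1. In 6.1.1 and 10.5.2, name the baseline visit for BCVA. Cohort A has two pre-operative values, so say which one is used. Keep the change from pre-operative baseline and state that it is a net effect that includes cataract removal.
2. In the same two sections, add a descriptive within-eye change in BCVA from the 24-month to the 36-month visit, by cohort, in the letter categories already used in 10.5.2. For Cohort A, say whether the value comes from the main visit or the washout visit, since Table 1 schedules BCVA at both.
3. With that table, report the distribution of the interval between the two visits (10 to 410 days under the windows) and the number of eyes with both values. Subjects withdrawn after a further glaucoma procedure (8.9.2) may have no 36-month value.
4. State that the table cannot show loss that occurred before 24 months.

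The cost is some wording and one extra table from BCVA already scheduled in both cohorts; no new visit or chart extraction is needed. The downside is that reported losses may look slightly less favourable.

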### 6.2 EFFECTIVENESS ENDPOINTS

For eyes that underwent washout prior to OMNI surgery:

- Reduction in mean unmedicated diurnal IOP (DIOP) from the preoperative unmedicated DIOP
- Reduction in mean number of IOP-lowering medications from screening
- Percent of eyes with a  $\geq 20\%$  reduction in unmedicated diurnal IOP from the preoperative unmedicated DIOP
- Percent of eyes with unmedicated diurnal IOP between 6 and 18 mmHg inclusive

[figure not shown]
For eyes that did not undergo washout prior to OMNI surgery:

- Reduction in mean medicated IOP from pre-operative medicated IOP
- Reduction in mean number of IOP-lowering medications from screening
- Percent of eyes with a  $\geq 20\%$  reduction in mean medicated IOP from pre-operative medicated IOP
- Percent of eyes with medicated IOP between 6 and 18 mmHg inclusive

[figure not shown]
[figure not shown]
[figure not shown]
[figure not shown]
7 [REDACTED]

7.1 [REDACTED]

b.

## 7.2 EXCLUSION CRITERIA

## 8 STUDY PROCEDURES

### 8.1 STUDY SCHEDULE – PRE-OPERATIVE WASHOUT (SUBJECTS THAT UNDERWENT MEDICATION WASHOUT PRIOR TO OMNI)

Table 1: Study Visit Schedule

*Note: The fellow eye should be followed per the PI's usual practice based on the ocular health of the fellow eye.*

PROCEDURE	RETROSPECTIVE DATA			OBSERVATIONAL PROSPECTIVE DATA			
	PRE-WASHOUT (DAY -45 TO -6)	POST-WASHOUT (DAY -6 TO 0)	OMNI SURGERY (DAY 0)	24 M  (DAY 700-1,040)	24 M WASHOUT  (DAY 700-1,040)	36 M (DAY 1,050-1,110)	36 M WASHOUT  (DAY 1,050-1,110)
Informed Consent and demographics 				X		X	
Medical & Ocular History	X	X		X	X	X	X
Medication Log 	X	X		X	X	X	X
Monocular BCVA 	X	X		X	X	X	X
Visual Field (Humphrey 24-2 SITA)	X			X		X	
IOP (Goldmann) 	X	X		X	X	X	X
Slit Lamp Exam	X	X		X		X	
Gonioscopy	X			X		X	
Dilated Fundus Exam/C:D Ratio	X			X		X	
Surgery			X				
Adverse Events	X	X	X	X	X	X	X

1.   

## 8.2 STUDY SCHEDULE – No PRE-OPERATIVE WASHOUT

**Table 2: Study Visit Schedule**

*Note: The fellow eye should be followed per the PI's usual practice based on the ocular health of the fellow eye.*

PROCEDURE	RETROSPECTIVE DATA		OBSERVATIONAL PROSPECTIVE DATA	
	PRE-SURGERY BASELINE (DAY -45 TO -6)	OMNI SURGERY (DAY 0)	24 M  (DAY 700-1040)	36 M (DAY 1,050-1,110)
Informed Consent and demographics 			X	
Medical & Ocular History	X		X	X
Medication Log 	X		X	X
Monocular BCVA 	X		X	X
Visual Field 	X		X	X
IOP (Goldmann) 	X		X	X
Slit Lamp Exam	X		X	X
Gonioscopy	X		X	X
Dilated Fundus Exam/C:D Ratio	X		X	X
Surgery		X		
Adverse Events	X	X	X	X

1. 

### **8.3 NUMBER OF SUBJECTS, DURATION OF FOLLOW-UP AND STUDY DURATION**

Up to 130 subjects will be enrolled. Eligible subjects will be enrolled at the 24-month follow up timepoint as shown by Table 1 or 2 as applicable. At least 50 subjects will be enrolled in each cohort. For subjects in cohort A, diurnal IOP measurements will be measured at both visits for those subjects who underwent medication washout and where DIOP was measured pre-operatively (Cohort A). Cohort A subjects using ocular hypotensive medication(s) at 24 and 36 months will undergo a medication washout (Table 3) and return for diurnal IOP measurements at a second visit within the same window, as shown in Table 1. There will be no diurnal IOP measurements for subjects in cohort B. IOP measurements will be measured as shown in Table 2.

It is anticipated that site initiation, recruitment and follow-up of subjects, data collection and site close-out will require approximately 60 months.

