## 8.7 PROSPECTIVE VISITS

After obtaining an understanding of the purpose of this study and reviewing and signing the ICD, all subjects will begin the prospective study visits. These visits should be performed according to the schedule provided in Tables 1 and 2. All attempts should be made to conduct each visit within the time interval specified in Tables 1 and 2. Evaluations conducted outside the prescribed time period will be considered protocol deviations.

[REDACTED]

[REDACTED]

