### 8.7.1 WASHOUT OF HYPOTENSIVE MEDICATIONS

Subjects who underwent washout prior to OMNI surgery (Cohort A) and who are taking hypotensive medications at the 24- and 36-month visits will be instructed to discontinue their ocular hypotensive medication regimen and to return for a post-washout visit after completing the appropriate washout period.

[REDACTED]

[REDACTED]

If the study subject fails to remember to not use ocular hypotensive medication for the study eye per the required washout period, they can restart washout and return for the

appropriate visit upon completion of washout and as long as it falls within the specified visit window. The minimum wash-out periods are specified in Table 3 below.

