### 10.2 ANALYSIS POPULATIONS

The intent-to-treat (ITT) analysis population includes all subjects who are enrolled and treated, regardless of whether or not they have a protocol deviation. The per-protocol analysis population (PP) is a subset of ITT, which includes all subjects who have canaloplasty and trabeculotomy after uneventful cataract surgery, 36-month IOP (or hypotensive medications washed out IOP if the medications can be washed out) and medication data, and have no clinically significant protocol deviations. It should be noted that the ITT subjects with an uneventful study procedure but with secondary surgical interventions (SSIs) before the 36-month visit will be included in the PP population even if they do not have the 36-month IOP and medication data.

The safety data will be summarized based on the ITT population.

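### At 36 months, Cohort A eyes on a 28-day drug must finish washout by the same Day 1,110 limit that governs the visit starting it, so first visits after Day 1,082 cannot give a compliant unmedicated DIOP

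*Combined protocol and SAP*

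**What the plan says.** Four rules in the combined protocol and SAP bear on this.

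- **Shared window.** Table 1 (Section 8.1) has a column headed "36 M (DAY 1,050-1,110" and gives the 36-month washout visit the same days. Section 8.3 says in words that Cohort A subjects on medication "will undergo a medication washout (Table 3) and return for diurnal IOP measurements at a second visit within the same window".
- **Start of washout.** Under Section 8.7.1, Cohort A subjects "who are taking hypotensive medications at the 24- and 36-month visits will be instructed to discontinue their ocular hypotensive medication regimen" and come back once the washout is complete. A subject who forgets and uses drops may restart, with the return visit "upon completion of washout and as long as it falls within the specified visit window".
- **Length of washout.** The periods in Table 3 are minimums. They are 28 days for the listed beta blockers, prostaglandin analogs, netarsudil and all listed combinations; 14 days for alpha agonists; and 5 days for carbonic anhydrase inhibitors and pilocarpine.
- **Consequence of lateness.** Section 8.7 says "All attempts should be made to conduct each visit within the time interval specified in Tables 1 and 2" and adds "Evaluations conducted outside the prescribed time period will be considered protocol deviations".

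Section 5 also ends follow-up at Day 1,110. Section 10.2 requires, for the per-protocol (PP) population, "36-month IOP (or hypotensive medications washed out IOP if the medications can be washed out) and medication data", and no clinically significant deviation.

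**The concern.** The first visit may fall on any day to Day 1,110, yet the washout that it triggers must also be finished by Day 1,110. For a subject on a 28-day drug who is seen late in the window, the site has three courses: hold the second visit late (a deviation), shorten the washout below the Table 3 minimum, or have no post-washout value.

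Three of the four Cohort A effectiveness endpoints in Section 6.2 use unmedicated DIOP, and Section 10.4 analyses this cohort separately. Only eyes still on drops at 36 months need the second visit. Any late, shortened or missing value therefore falls on those eyes and not across the cohort as a whole. Those eyes have needed drops after surgery, so losing them selectively could flatter the unmedicated results. A subject first seen after Day 1,082 would also stop treatment for four weeks to produce a measurement that the protocol classes as a deviation.

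**Working it through.** The documents state no figure for this, so there is none to reproduce. The check is calendar arithmetic.

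**Inputs.** 36-month window, Day 1,050 to 1,110 inclusive, for both visits (Table 1, Section 8.3). 24-month window, Day 700 to 1,040 inclusive (Table 1). Minimum washouts of 28, 14 and 5 days (Table 3).

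**Formula.** Latest workable first visit = window end − washout length. Permitted days = end − start + 1.

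**36 months, no restart.** Permitted days: 1,110 − 1,050 + 1 = 61.

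| Minimum washout | Latest workable first visit | Days that work | Days that do not |
|---|---|---|---|
| 28 days | 1,110 − 28 = 1,082 | 33 of 61 (54.1%) | 28 of 61 (45.9%) |
| 14 days | 1,110 − 14 = 1,096 | 47 of 61 (77.0%) | 14 of 61 (23.0%) |
| 5 days | 1,110 − 5 = 1,105 | 56 of 61 (91.8%) | 5 of 61 (8.2%) |

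If the visit day counts as washout day 1, the 28-day figure becomes 27 of 61 (44.3%), so the convention hardly matters.

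**36 months, 28-day drug, restart after k lost days.** Latest workable first visit = 1,110 − 28 − k.
- k = 7: Day 1,075, 26 of 61 days (42.6%)
- k = 14: Day 1,068, 19 of 61 days (31.1%)
- k = 28: Day 1,054, 5 of 61 days (8.2%)

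**24 months, 28-day drug.** Permitted days: 1,040 − 700 + 1 = 341. Latest workable first visit: 1,040 − 28 = 1,012. Days that do not work: 28 of 341 (8.2%). The difficulty belongs to the short 36-month window.

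**With the washout visit allowed to Day 1,110 + 28 = 1,138.** Latest workable first visit for a 28-day drug = 1,138 − 28 − k = 1,110 − k.
- No restart: Day 1,110, 61 of 61 days
- k = 7: Day 1,103, 54 of 61 days (88.5%)
- k = 14: Day 1,096, 47 of 61 days (77.0%)
- k = 28: Day 1,082, 33 of 61 days (54.1%)

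A full 28-day restart thus still needs a first visit by Day 1,082, which is why the extension should be paired with a booking target.

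**The case against.** The strongest reply is that this is a scheduling matter. The rules can all be met together: a site that reads Section 8.3 with Table 3 will see that a subject on a 28-day drug should attend by Day 1,082, and 33 days remain for that. The subjects are the sites' own patients (Section 8.5) and have a 24-month medication log, so sites can identify them in advance. This stands. A reader might infer that the protocol contradicts itself, and it does not.

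Second, text is missing where advice on timing would sit: Table 1 footnote 2 on the washout columns, and redacted blocks in Sections 8.7 and 8.7.1. Early booking may already be advised there. This also stands, and the finding is limited to the readable text. A hidden extension of the window is less likely, because the readable restart sentence keeps the window as the limit.

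Third, harm is not shown. ITT keeps subjects with deviations, PP drops only clinically significant ones, no visible rule discards a late value, and Section 10.1 calls the study descriptive. This stands against any claim of bias. It does not settle whether a DIOP made late only by Table 3 counts as clinically significant for PP, which the readable text leaves open.

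A reader might also take the pre-operative columns of Table 1 as proof of an oversight, since there the second visit has its own window, "POST-WASHOUT (DAY -6 TO 0". That comparison does not help. Pre-washout runs from Day -45 to -6, which is 40 days. A 28-day washout ending by Day 0 must start by Day -28, so Days -27 to -6 (22 of 40) could not fit it either. Those visits are also retrospective chart data anchored to surgery.

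**Conclusion.** The point holds in a limited form. On the readable text, a Cohort A eye on a 28-day drug that is first seen on Day 1,083 to 1,110 cannot give a compliant 36-month unmedicated DIOP, and the restart rule narrows the usable days further. The consequence is a risk of deviation, PP exclusion or loss that falls only on still-medicated eyes.

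Two stronger readings are tempting and unsupported. One is that about 46% of these subjects would be affected: 28 of 61 counts calendar days, and the documents give neither the number of eyes on 28-day drugs at 36 months nor when subjects attend. The other is that the 36-month results will be biased: nothing shows that sites would book late, shorten washouts or skip visits, and late values stay in ITT.

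The conclusion assumes that the missing text neither extends the window nor sets an earlier limit for the first visit. Severity is minor to moderate. It is worth acting on mainly because the remedy is cheap.

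**What to change.** - In Table 1, Section 8.3, the restart sentence of Section 8.7.1 and the follow-up statement in Section 5, let the 36-month washout visit alone run to Day 1,138 for every Cohort A subject who needs a washout. One end date is enough. Drug-specific dates would add complexity, and Table 3 gives no period for drugs under its residual heading, where sites contact the sponsor.
- Leave the 36-month visit window and all Table 3 periods unchanged.
- In Section 8.7.1, ask sites to aim to see subjects on 28-day drugs by Day 1,082, so that a full restart can fit (1,082 + 28 + 28 = 1,138).
- In Section 10.2, assign each post-washout DIOP to the 36-month visit that started the washout.
- Make no change at 24 months.

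The cost is one column heading, a clause in each of three sections, two added sentences, and IRB review as necessary under Section 13. The downside is that some 36-month DIOPs will be taken up to 28 days after Day 1,110.
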